3.4.2 Inference

Uncertainty will be reported using confidence intervals, standard errors of estimates and the corresponding p-values.

3.4.3 Robustness Checks

Several robustness checks will be implemented, including the following:

- We will test the common support in the matched sample and the t-test after matching to analyse if the matching is satisfactory, including reviewing the B and R – Rubin to ensure that the matching matches at least well.
- Use Rosenbaum (2002) to evaluate to what extent the ATE estimate is robust to non-compliance with the assumption of selection in observables.
- Measure the sensitivity to the matching method to test the robustness of the main matching technique one-to-one. Different forms of matching will be estimated: (a) calliper (with different widths), (b) nearest neighbour (NN) (tested with five neighbours), and finally, (iii) kernel. The choice of the matching method will be transparently discussed and linked to the present evaluation.
- Estimate the results using the Inverse Probability Weighting (IPW) methodology and Entropy Balancing.
- We will first apply the balance test proposed by Smith and Todd (2005) based on the regression of the covariates against the treatment variable (T) and its polynomial forms, where $p(X)$ rejecting the null hypothesis would imply that the variables X_j are unbalanced between the groups. Second, we will implement a Kolmogorov-Smirnov test to ensure a balance between both groups.
- We will consider, if applicable, the falsification test proposed by Lee and Lemieux (2010)). This test seeks to test the hypothesis that the average effect is zero in covariates or in pseudo-outcomes on which - by definition - no effect of the treatment.

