	70	0.1272	0.1284	0.1298	0.1317	0.1341
	60	0.1374	0.1385	0.1402	0.1422	0.1449

Rationale for Targeting 100 Schools

Targeting 100 schools and 16,000 students is justified by several considerations. First, a larger pool of schools increases the likelihood of recruiting a diverse population of school types (e.g., school-level of deprivation, FSM, different socioeconomic backgrounds) and student demographics, enabling robust subgroup analyses and generalizability of findings across various contexts. Second, a large overall sample size enhances statistical power to detect smaller but potentially meaningful intervention effects, minimising the risk of false negatives and providing reliable findings to inform future interventions. Third, the target sample size was selected to ensure sufficient power for the quasi-experimental design (QED) analysis focused on a targeted subgroup of students. Lastly, a larger sample size accommodates the cluster randomised trial design, accounting for potential clustering effects and maintaining adequate power for the primary analysis.

Table 4 displays the minimum detectable effect in the protocol according to the assumed parameters, target sample size, and the respective effect size after randomisation driven by the achieved number of responses on the primary outcome. Thus, while the MDES in the protocol is an estimation from the assumptions, the MDES estimated in the column 'Randomisation' corresponds to the actual achieved sample size at baseline in the primary outcome from the schools that were randomised. As we are adopting an intention-to-treat approach, the estimation includes responses from 4 schools that dropped out after randomisation.⁵ Those four schools that dropped out belong to the intervention group.

⁵ This means that now the number of schools in the trial are 74 with 4 dropping out from the intervention group after randomisation

Table 4 Sample size calculations and effects size

		Protocol	Randomisation
Minimum Detectable Effect Size (MDES)		0.1064	0.094
Pre-test/ post-test correlations	level 1 (participant)	n/a	n/a
	level 2 (cluster)	n/a	n/a
Intracluster correlations (ICCs)	level 1 (participant)	n/a	n/a
	level 2 (cluster)	0.03	0.015
Alpha		0.05	0.05
Power		0.8	0.8
One-sided or two-sided?		Two-sided	Two-sided
Average cluster size		160⁶	166⁷
Number of clusters	intervention	50	40
	control	50	38
	Total	100	78 ⁸

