3.1 Design overview

A QED study, using a propensity score matching design, will be embedded within this trial to examine the targeted element of the intervention. In the intervention arm, some staff are given advanced training (Diploma level) to identify a more vulnerable CYP subgroup and provide extra targeted support. This individual intervention is estimated to be provided to about 75 CYP per school, 15 CYP per year group. In the main trial analysis, this group of CYP in Year 8 would become subsumed into the overall intervention group, with all baseline and follow-up data collected on outcomes included in the main trial. Staff who participate in the diploma training will already have identified most young people who would potentially benefit from more intensive support and, in the early stages of training, will be provided with tools to identify any additional young people. By the time of follow-up, at 15 months, this cohort of young people would have been identified and received at least nine months of intervention.

Assuming this group of vulnerable young people is about 15 per school, with a consent rate of 80%, the effective sample size will be 12 per school. Assuming our original aim of 100 schools in the trial, this gives 1,200 CYP across all schools, 600 in the treatment arm matched to 600 in the control arm.

The outcomes for this study will be the same individual pupil-level primary and secondary outcomes as for the main trial, for those that are provided with this individual or small group support in Year 8: the primary outcome is externalising behaviour at pupil level measured by the Strengths and Difficulties Questionnaires (SDQ) – Combined Conduct and Hyperactivity Scale. The secondary outcomes at pupil levels consist of internalising behaviour, prosocial behaviours, total difficulties, non-psychotic psychological distress, well-being, sense of connectedness, exclusions and suspensions, and school attendance.

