3.2 Sample size calculations

Sample size estimation and assumptions

The sample size calculation is designed to detect a difference of 0.2, YEF's expected maximum MDES value for efficacy evaluations. To detect this difference with 80% power, an alpha of 0.05 and a two-sided test, at least 527 CYP in each group are required, totalling 1,054 CYP.

For the PSM, the sample size estimations starts from the assumption of 15 CYP on average per school at baseline, assuming a follow-up rate of 80% to account for attrition and consent. The harmonic mean of CYP per year group receiving more intensive support is estimated to be 15. Using this and an ICC of 0.03, the estimated clustered design effect is 1.45. This inflates our required sample to 1,528. With 100 schools, 15 participants per class provide a sample of 1500. Incorporating the inverse propensity score weights will reduce the size of the overall sample by a conservative estimate of 30%, resulting in a required sample of 1,070.

Table 7 indicates the impact of different group sizes (pupils per cluster) on the number of schools needed in the intervention arm of the PSM analysis. The table shows that with 15 pupils per cluster, data from at least 36 intervention schools are required. At the lower end, with 10 pupils per cluster, data from 48 schools would be required. If the follow-up rate is 80% as anticipated, 12 pupils per school will be available, requiring circa 42 schools in each arm of the study. While the target is to maintain 50 schools in each arm, these conservative estimates should be considered.

At the point where the PSM is conducted, the pre- and post-test correlation for the primary outcome can be estimated and incorporated into the sample size calculation, potentially adjusting the required sample size.

Table 7 Impact of differential cluster size on the proportion of schools retained for the intervention group

Pupils	15	14	13	12	11	10
Base sample	527	527	527	527	527	527
Design effect (DE)	1.45	1.42	1.39	1.36	1.33	1.30
Adjusted sample	764	748	733	717	701	685
Sample adjusted for IPW	535	524	513	502	491	480
Number of intervention schools	36	37	39	42	45	48

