Table 8 displays the effect size based on the assumption of 12 CYP per cluster at follow-up, assuming 15 at baseline, accounting for attrition and consent. This is a conservative estimate. The second column "Randomisation" displays the effect size assuming 12 CYP per cluster given the number of schools achieved and the observed ICC at baseline. Thus, the total number of participants is an estimation.

Table 8 Sample size calculations - QED

		Protocol	Randomisation
Minimum Detectable Effect Size (MDES)		0.17	0.20
Pre-test/ post-test correlations	level 1 (participant)	n/a	n/a
	level 2 (cluster)	n/a	n/a
	level 1 (participant)	n/a	n/a

		Protocol	Randomisation
Intracluster correlations (ICCs)	level 2 (cluster)	0.03	0.015
Alpha		0.05	0.05
Power		0.8	0.80
One-sided or two-sided?		Two	Two
Average cluster size (if clustered)		12	12
Number of clusters (schools)	Intervention	50	40
	Control	50	38
	Total	100	78
Number of participants	Intervention	600	456
	Control	600	480
	Total	1,200 (without weighting)	936

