The propensity score is the probability of receiving the intervention conditional on measured participant covariates. It is, in essence, a balancing score. If we have two populations, the intervention and control populations, both of which have a similar propensity score, the distribution of baseline covariates will be the same in the intervention and control groups. Hence, we can remove confounding effects by comparing participants who share a propensity score. This is analogous to that induced by randomisation in RCTs.

For the propensity score, the covariates for the matching will be socio-demographic variables such as sex, age, ethnicity, FSM, attendance, exclusions, suspensions and pre-test outcomes for the primary and secondary outcomes. As is often the case in PSM, the selection of the variables will depend on which model delivers the best balance in the matched sample.

A counterfactual control group will be derived using PSM to draw causal inferences of the relative effect of the intervention. A probit regression model will be employed. Callipers of width 0.2 of the standard deviation of the width of the logit propensity score will be employed to maximise matching. Once the propensity scores have been generated, they will be incorporated into the primary and secondary analysis using inverse propensity score weights (IPSW), because this will reduce the sample size required for the control group. One potential limitation of weighting approaches, akin to Horvitz-Thompson's estimation, is the potential for a substantial increase in variance when dealing with extreme weights (i.e. when estimated propensity scores approach 0 or 1). This increased variance is justified if the model is

appropriately specified and the weights are accurate. However, a concern arises when some extreme weights are more closely linked to the estimation process rather than the true underlying probabilities. To mitigate the impact of extreme weights, we would consider weight trimming as a solution, whereby weights exceeding a certain maximum value are capped at that maximum (Stuart, 2010). Robustness check through other matching techniques will allow us to test the sensitivity of this approach to increase in variance. Other matching approaches will include exact matching, Nearest-Neighbour matching, Mahalanobis distance, PSM with different calliper widths, and CEM, as discussed further in section 3.4.3 below.

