3.4.1 Primary analysis

The primary analysis will likely be a linear regression model adjusted for baseline stratification covariates (proportion FSM), and the baseline value of the outcome. As there is variation in

business as usual (BAU) across sites, a multilevel model will be estimated to account for pupils being nested within schools. Individual outcomes will be incorporated into the model with an inverse propensity weight for each participant.

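### The QED is described and sized as one-to-one matching, which would leave about 12 of 13 control pupils unused; up to five controls per supported pupil would lower the MDES from 0.20 to 0.16 at best, and the primary estimator needs to be stated once

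*SAP*

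**What the plan says.** On matching, a SAP 3.4.3 bullet reads "Measure the sensitivity to the matching method to test the robustness of the main matching technique one-to-one". The alternatives it lists include other callipers, five nearest neighbours and kernel matching. Inverse probability weighting and entropy balancing appear as further checks.

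On size, SAP 3.1 plans "600 in the treatment arm matched to 600 in the control arm". In SAP 3.2, "Table 8 displays the effect size based on the assumption of 12 CYP per cluster at follow-up". The Randomisation column of Table 8 has 40 and 38 schools, 12 pupils per school in each arm, 936 pupils in total, ICC 0.015 and an MDES of 0.20. SAP 3.2 treats 0.2 as the largest MDES the funder expects of an efficacy evaluation.

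On the estimator, SAP 3.3 first derives a comparison group by propensity score matching within a calliper of 0.2 SD, then carries the scores into the analyses as inverse weights. SAP 3.4.1 says "Individual outcomes will be incorporated into the model with an inverse propensity weight for each participant". Protocol Appendix 2 says the same. SAP 3.4.5 speaks of obtaining a matched sample and, from it, the average effect on the treated (ATET).

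On available controls, SAP Table 6 gives 6,179 control pupils with a baseline primary outcome.

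**The concern.** Supported pupils are scarce, at about 12 per intervention school. Control pupils are plentiful, and their outcomes are collected for the main trial anyway. Keeping one control per supported pupil makes the control side of the comparison as imprecise as the treated side, for no saving in fieldwork.

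The QED has no margin to spare. Its MDES in Table 8 is already 0.20, and that counts all 40 intervention schools. SAP 2.2 reports four schools lost after randomisation: "Those four schools that dropped out belong to the intervention group". The SAP also leaves open whether the headline estimate comes from a one-to-one matched sample, a weighted sample, or a matched sample that is then weighted. Table 8 therefore cannot be tied to a defined analysis.

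**Working it through.** **Share of controls used.** Supported pupils: 40 × 12 = 480. Controls with a baseline score: 6,179 (Table 6). 6,179 / 480 = 12.9, so one-to-one matching leaves about 12 of 13 (92%) unused. Table 4 instead puts 7,214 in the control row, which gives 15.0, or about 14 of 15 unused. Table 6 is the more credible source: 6,179 + 7,214 = 13,393, the total stated in Table 4, whereas Table 4's own rows sum to 6,391 + 7,214 = 13,605. If only 80% of the 6,179 were followed up, 4,943 would remain, still 10.3 per supported pupil.

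**Formula.** The two-level MDES of SAP 2.2 without covariates, written by arm:

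MDES = M × √{[ρ + (1−ρ)/m_T]/J_T + [ρ + (1−ρ)/m_C]/J_C}, with M = t(0.975) + t(0.80) on J−2 degrees of freedom. For 78 schools M = 2.838.

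**Reproducing Table 8.** J_T = 40, J_C = 38, m_T = m_C = 12, ρ = 0.015:
0.015 + 0.985/12 = 0.0971; 0.0971/40 + 0.0971/38 = 0.00498; √ = 0.0706; × 2.838 = **0.200**. The stated 0.20 is confirmed.

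**Five controls per supported pupil.** m_C = 5 × 480/38 = 63.2:
0.015 + 0.985/63.2 = 0.0306; 0.0971/40 + 0.0306/38 = 0.00323; √ = 0.0569; × 2.838 = **0.161**.

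The same formula with k × 12 × J_T controls spread over 38 schools:

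| Schools | ICC | 1:1 | 1:3 | 1:5 | All 6,179 controls |
|---|---|---|---|---|---|
| 40 + 38 | 0.015 | 0.198 | 0.168 | 0.161 | 0.155 |
| 36 + 38 | 0.015 | 0.208 | 0.176 | 0.169 | 0.162 |
| 40 + 38 | 0.03 | 0.212 | 0.185 | 0.179 | 0.173 |

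(The 0.198 differs from 0.200 because 480 controls over 38 schools is 12.6 per school, not 12.) These are best-case values. They assume that every supported pupil finds the full number of distinct controls within the calliper. At 1:5 that means 2,400 controls, or 39% of 6,179.

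**Allowing for unfound matches.** The documents give no selection strength, so this step rests on assumptions: five correlated baseline covariates, a propensity model with AUC 0.66–0.84, the 0.2 SD calliper and controls weighted 1/k.
- The standard error fell by 11–17% at up to five controls. That gives 0.200 × 0.83 = 0.166 to 0.200 × 0.89 = 0.178, or about 0.17–0.18. Further runs at AUC 0.65–0.79 gave falls of 13–20%.
- Under strong selection only about 3.7 matches per pupil were found. The gain was then about 11%, no more than at 1:3.
- Bias was at most 0.005 outcome SD. The further runs reached 0.007, against a standard error of 0.048.
- The mean largest covariate imbalance fell from 0.04–0.05 to about 0.02 SD. Under another assumed set-up the fall was smaller (0.071–0.079 to 0.057–0.066), and systematic imbalance at 1:5 reached about 0.012 SD under the strongest selection.
- Distance on the score itself widened slightly. The residual difference was at most 0.001 SD at 1:1 and 0.001–0.007 at 1:5 with the calliper. Without a calliper it was 0.02–0.31 at 1:5, so the calliper is essential.

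**The case against.** The strongest objection is that one-to-one is not clearly the primary analysis. The phrase occurs once, inside a robustness bullet, while the sections that define the analysis, and Protocol Appendix 2, specify inverse propensity weights. If every control pupil is weighted, none is discarded. The 600:600 and 936 figures are planning estimates, not analysis rules. A reader might therefore infer that the plan definitely discards 12 of 13 controls, and the documents do not establish that. They do contain a conflict. SAP 3.3 matches first and weights afterwards, so if the match is one-to-one, weighting cannot bring back the dropped controls. If weighting of the full control arm is intended, then 3.4.3, 3.1 and Table 8 misdescribe the analysis and its MDES. The same sections need editing either way.

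A second objection is that five-neighbour matching is already planned as a check, so that estimate will be produced, and SAP 3.3 regards the literature as undecided between algorithms. This stands. The point concerns which estimate is the headline, a bias–variance choice, and it is not an error in the plan.

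A third concerns balance. A reader might infer that five controls give better balance, or that the precision comes free. Nothing in the documents shows this. In simulation the largest covariate imbalance fell because chance differences average out over more controls, but the matches lie somewhat further away on the score, and the size of each effect depends on assumed selection.

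**Conclusion.** The point holds as a cheap improvement. As described in SAP 3.4.3 and sized in SAP 3.1 and Table 8, the QED would use one control per supported pupil and leave about 12 of 13 unused (Table 6 count). On the Table 8 inputs the MDES is 0.20 at one-to-one and 0.16 at best with five controls. About 0.17–0.18 is more realistic under the assumed selection strengths. If the four lost intervention schools supply no supported pupils (an assumption), one-to-one gives 0.208, above the 0.20 limit, and 1:5 gives 0.169 at best.

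The 0.16 follows from the SAP's own formula and inputs. The 0.17–0.18, the negligible added bias and the finding that covariate balance is no worse rest on simulation with assumed covariates and selection, and on keeping the calliper.

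**What to change.** In SAP 3.3, 3.4.1 and 3.4.3, state one primary estimator, in the same words. Make it variable-ratio matching of up to five control pupils per supported pupil within the stated calliper, with controls weighted 1/k within each matched set of k, so that it targets the ATET named in 3.4.5. Keep one-to-one matching and inverse propensity weighting as robustness checks.

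Restate the Table 8 MDES for that estimator, with the assumed number of matches found. Two entries should be corrected at the same time:
- The Randomisation participant rows appear swapped: 40 × 12 = 480 intervention and 38 × 12 = 456 control, but the table prints 456 and 480.
- The Protocol-column MDES of 0.17 does not follow from 12 per school at ICC 0.03, which gives 0.188. It matches 15 per school (0.174).

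The cost is SAP wording and one matching option, with no new data. The downside is that later matches lie slightly further away on the propensity score; the calliper and the balance report already planned in SAP 3.3 control this.

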3.4.4 Secondary analyses

Secondary outcomes will be assessed similarly by examining the variable distribution by establishing diagnostic plots to identify the most appropriate regression approach, including

stratification factors and baseline covariates within a multilevel model. Diagnostic plots are graphical tools used to assess the assumptions and fit of a statistical model. These may include residual plots (e.g., residuals vs. fitted values, normal Q-Q plots) to check for non-linear patterns, unequal variance, outliers, and normality assumptions. Partial regression plots can be used to examine the relationship between the outcome and specific predictors, while leverage plots help identify influential observations. Additionally, added variable plots can assess the linearity assumption between the outcome and predictors.

Based on the patterns observed in these diagnostic plots, we may consider transformations, robust regression techniques, or alternative model specifications to address potential violations of assumptions. The stratification factors, such as the binary indicator for the percentage of pupils eligible for free school meals, and baseline covariates, like the baseline measure of the outcome variable and other relevant demographic or school-level characteristics, will be included as predictors in the multilevel model to account for clustering and adjust for potential confounding effects.

3.4.5 Subgroup analyses

Sub-group analysis will be conducted to estimate how the treatment effects vary within groups. This means estimating heterogeneous effects, namely, conditional average treatment effects (CATE). The groups consist of sex, ethnicity and FSM. We will aim to minimise the number of strata within each category whenever applicable and necessary. For example, ethnicity will be divided into minority and non-minority to maximise statistical power.

After passing the balancing test and robustness checks, the approach will first achieve a matched sample, thus obtaining the average treatment effect on the treated (ATET). Then, we will condition the ATET on the respective group variables to obtain treatment effect by stratum, namely the CATE.

3.4.6 Further analyses

There is no further analysis beyond the sub-group analysis discussed above and the robustness checks.

3.4.7 Treatment effects in the presence of non-compliance

We will not conduct any Complier Average Causal Effects (CACE) analysis for this strand of the study. The nature of the targeted support for this sub-group presents significant challenges in measuring compliance, such as the whole school intervention. This targeted intervention is highly personalised and adaptable to the individual needs of each student, which means that the intensity and frequency of engagement can vary greatly.

3.4.8 Missing data

As the generation of intervention and comparison groups are based on complete data, we do not account for missing data.

